### *Expected relevance*

Therapeutic alliance during the acute phase of psychotic illness is one of the most pressing obstacles for successful long term recovery (e.g. Cavelti et al., 2016). In order for patients to accept much-needed medication and psychosocial therapy and not drop out prematurely, intrinsic motivation to adhere to therapy is crucial. Motivational Interviewing is a method, that has been developed and evaluated over the last three decades and that shows promising results, not only for patients with addiction but also for other patients who struggle with compliance and ambivalence towards treatment and change of behavior. For further information on the method see chapter 3.4. *Study intervention*.

At the same time, it is well known from clinical experience that patients are offered psychotherapy only late during the course of hospitalizations and not when it is most needed – during the acute phase of their illness. Accordingly, there is a clear gap in the literature as to which interventions are particularly useful in this challenging yet crucial phase of the illness.

We believe that the current project and the psychotherapeutic interventions tested here, can provide valuable data on acceptance, feasibility and effectiveness of such interventions and which can then be used to supplement a large multicentre trial across Switzerland.

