## **2 STUDY OBJECTIVES AND DESIGN**

### **2.1 Hypothesis and Objectives**

The **primary objective** of the study is to investigate the impact of a brief intervention with Motivational Interviewing in an acute psychiatric inpatient setting on factors that impact treatment outcome such as therapeutic alliance and adherence to treatment.

The **second objective** is to examine if the effect of Motivational Interviewing can be measured in changes in symptom severity.

The **third objective** is to examine secondary effects of Motivational Interviewing on motivation for further psychotherapeutic treatment and higher expectations of self-efficacy after discharge from the hospital.

Therefore, the study grounds on three **hypotheses**:

1. Four sessions of psychotherapeutic intervention with motivational interviewing for newly admitted acute patients improves the therapeutic alliance and the adherence for treatment compared to supportive counseling.
2. Four sessions of psychotherapeutic intervention with motivational interviewing for newly admitted acute patients decreases symptom severity compared to supportive counseling.
3. Patients show higher motivation to seek psychotherapeutic treatment and have a higher self-efficacy expectation after leaving the inpatient stay, when they received an intervention with motivational interviewing compared to supportive counseling.

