### **2.2 Primary and secondary endpoints**

Primary endpoints are the therapeutic alliance as assessed with the *Scale to Assess Therapeutic Relationship STAR* (McGuire-Snieckus et al., 2007) and adherence to treatment as measured with the *Brief Adherence Rating Scale BARS* (Byerly et al., 2008). These variables will be measured before and after the study intervention or control intervention.

Secondary endpoints include changes in symptom severity as assessed with the *Positive and*

*Negative Symptom Scale PANSS* (Kay et al., 1987), as well as the motivation for psychotherapy (measured with the German version of the *Questionnaire to measure the motivation for psychotherapy* by Schulz et al., 1995) and self-efficacy (measured with the *General Self-Efficacy Scale* by Schwarzer & Jerusalem, 1995). All secondary variables will be measured before and after the study intervention or control intervention.

As this study (risk category A) does not include drugs or other medical products and patients are hardly exposed to any more risks than in routine clinical care, no safety endpoints are defined.

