#### Psychometric tests used in the study

Primary diagnosis at point of admittance and medical history are assessed by physicians and psychologists at PUK and documented electronically. The applicant and master's students enrolled in the project will use this available data and document them in specific study protocols. These assessments are part of standard assessments at the hospital by physicians and psychologists. For primary psychiatric diagnoses the International Classification of Diseases (ICD-10) is used.

- Psychotic symptoms are assessed with the *Positive and Negative Syndrome Scale* (PANSS). This is a structured interview, which consists of four scales measuring positive and negative syndromes of schizophrenia, their differential, and general severity of illness.
- Two cognitive tests: Letter-Number-Span (LNS), Symbol-Coding-Test (SCT) from MATRICS (Measurement and Treatment Research to Improve Cognition in Schizophrenia, Consensus Cognitive Battery; Nuechterlein et al., 2008)
- The *Brief Adherence Rating Scale* BARS (Byerly et al, 2008) is a brief, pencil-paper, clinician-administered adherence assessment instrument. It consists of 4 items: 3 questions and an overall visual analog rating scale to assess the proportion of doses taken by the patient in the past month (0%–100%).
- The therapeutic relationship will be evaluated with the *Scale to Assess Therapeutic Relationship* STAR (McGuire-Snieckus et al., 2007). The patient (STAR-P) and clinician scales (STAR-C) each have 12 items comprising three subscales: positive collaboration and positive clinician input in both versions, non-supportive clinician input in the patient version, and emotional difficulties in the clinician version.
- Motivation for psychotherapy will be measured with the *Fragebogen zur Erfassung der Psychotherapiemotivation* (FPTM; engl: "Questionnaire to measure the motivation for psychotherapy") by Schulz, Nübling und Rüdell (1995), a 4-point Likert-scale with 39 items.
- Self-efficacy is measured with the German version of the *General Self-Efficacy Scale* (GSE) by Schwarzer & Jerusalem (1995), an instrument that has been proved with a sample of more than 19'000 persons in 25 countries and shows good psychometric properties.

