## 4 STATISTICS AND METHODOLOGY

### 4.1. Statistical analysis plan and sample size calculation

Hypothesis 1: Four sessions of motivational interviewing for newly admitted acute patients (within the first 7 days of hospitalization) improve the therapeutic alliance and the adherence for treatment compared to supportive counseling.

Statistical analysis for hypothesis 1: To apply the statistically most sensitive test, we will use an ANCOVA to analyze the treatment effect of motivational interviewing compared to supportive counseling, with baseline values used as covariates.

Hypothesis 2: Four sessions of motivational interviewing for newly admitted acute patients decreases symptom severity compared to supportive counseling.

Statistical analysis for hypothesis 2: We will use an ANCOVA to analyze the treatment effect of motivational interviewing compared to supportive counseling, with baseline values used as covariates.

Hypothesis 3: Patients show higher motivation to seek psychotherapeutic treatment and have a higher self-efficacy expectation after leaving the inpatient stay, when they received an intervention with motivational interviewing compared to supportive counseling.

Statistical analysis for hypothesis 3: We will use an ANCOVA to analyze the treatment effect of motivational interviewing compared to supportive counseling, with baseline values used as covariates.

Additional calculations: We also want to investigate how the number of hospitalization days and the severity of symptoms at the beginning of the intervention have an influence on the therapy outcome. We calculate this with a multiple regression with days of hospitalization and/or the PANSS total score as independent variables. The treatment outcome is defined as the delta between symptoms before and after the intervention and serves as dependent variable.

General statistical considerations: We will use routine procedures of data processing and use data transformation if necessary (in case of non-normal distribution). Standard statistical calculations will be computed. The level of significance will be set to  $p < 0.05$  (two tailed). Effect sizes will be calculated for significant results. The IBM® SPSS Statistics® statistical software as well as the program R will be used.

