Sample size justification: Comparable studies found effect sizes that were moderate (Cohen's  $d = 0.3 - 0.5$ ). An effect sizes of  $f = 0.25$  will require us to recruit at least 64 patients per group to achieve 80% power and to detect such an effect with reasonable certainty at an alpha level of 0.05. We therefore plan to include a minimum of  $N = 128$  patients (calculated with G\*Power 3.1).

Analysis population: There is only one analysis population for all hypothesis. For inclusion criteria see chapter 4.1.

Analysis of gender differences: Analyses of gender differences are not planned because there is no research evidence to suggest that gender may be a determining variable. However, it is planned to conduct a group comparison between patients who benefit strongly from MI and those who benefit little, and to investigate possible discriminatory factors as part of this.

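### Effect sizes are planned for significant results, which would bias the estimates this pilot passes on; the rule for Hypothesis 1 and the primary STAR score also need stating

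*Combined protocol and SAP*

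**What the plan says.** **Reporting.** Under general statistical considerations, section 4.1 states: "Effect sizes will be calculated for significant results". No section promises an estimate or confidence interval for an endpoint that misses significance.

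**Primary endpoints.** Section 2.2 begins "Primary endpoints are the therapeutic alliance as assessed with the" STAR and adds BARS for adherence. Hypothesis 1 joins the two: MI "improves the therapeutic alliance and the adherence for treatment compared to supportive counseling" (section 2.1), repeated in section 4.1 as "improve the therapeutic alliance and the adherence for treatment compared to supportive counseling". The analysis is an ANCOVA adjusted for baseline; one ANCOVA per endpoint is my reading. "The level of significance will be set to" p < 0.05, two-tailed. I found no success rule, ordering, alpha split or multiplicity adjustment.

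**STAR.** Section 3.3, on psychometric tests, says: "The patient (STAR-P) and clinician scales (STAR-C) each have 12 items comprising three subscales". No section says which version, total or subscale is primary.

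**Power.** The sample size paragraph of section 4.1 cites effects of d = 0.3 to 0.5 from comparable studies, takes f = 0.25 and asks for at least "64 patients per group to achieve 80% power and to detect such an effect with reasonable certainty at an alpha level of 0.05". It ties this to no endpoint.

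**Use of the results.** Section 1 (Expected relevance) hopes for data that "can then be used to supplement a large multicentre trial across Switzerland", and section 6.2 also presents the pilot as groundwork for larger studies.

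**The concern.** A pilot's most useful output is an estimate with its uncertainty. If a standardised effect is calculated when p < 0.05 and not otherwise, the calculated effects come from trials in which chance helped, so they run high on average. A planner who sizes the next trial on them will make it too small. An endpoint that missed significance may still hold a useful effect, but the plan commits to no figure for it.

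The other gaps concern interpretation. With two primary endpoints, several possible STAR scores and no stated rule, the standard for Hypothesis 1 could be settled after the data are seen. The 80% power might also be read as the power for Hypothesis 1 as a whole, which it is only if a single endpoint decides the matter.

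**Working it through.** **Inputs from the documents:** 64 per group, 1:1 allocation, f = 0.25 (d = 2f = 0.5), two-sided alpha 0.05, ANCOVA with one baseline covariate, cited range d = 0.3 to 0.5.

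**Assumptions, not in the documents:** baseline-outcome correlation r of 0 or 0.5; correlation between the two endpoints 0 to 0.7; the cited d is unadjusted; d and r are the same for both endpoints.

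**1. The plan's own figure.** Noncentral F with noncentrality N × f² = 128 × 0.0625 = 8 and 1 and 125 degrees of freedom gives power 0.801. N = 128 reproduces as a single two-sided test.

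**2. The filter.** At r = 0 the standard error of the standardised difference is √(2/64) = 0.177. The critical t on 125 df is 1.979, so the smallest effect that can be significant is 1.979 × 0.177 = 0.350. A true d of 0.3 can therefore be reported only as something larger.

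The mean of the significant estimates is approximately d + SE × φ(k) / [1 − Φ(k)], with k = 1.979 − d/SE. For d = 0.5, k = 1.979 − 2.828 = −0.849, which gives 0.5 + 0.177 × 0.347 = 0.56. Simulation with the t distribution (2,000,000 runs) gives:

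| True d | Mean d if significant, r = 0 | None calculated, r = 0 | Mean d if significant, r = 0.5 | None calculated, r = 0.5 |
|---|---|---|---|---|
| 0.3 | 0.48 | 61% | 0.43 | 51% |
| 0.4 | 0.51 | 39% | 0.47 | 26% |
| 0.5 | 0.57 | 20% | 0.53 | 10% |

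The columns headed none calculated are 1 minus the single-test power; at r = 0 that power is 0.391, 0.612 and 0.801. For r = 0.5 the effect on the test scale is d/√(1 − r²).

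**3. If either endpoint sufficed, unadjusted.** With independent endpoints the two-sided familywise error is 1 − 0.95² = 9.75%. Simulation gives 9.8%, 9.1% and 8.4% at endpoint correlation 0, 0.5 and 0.7. The chance of a false result in favour of MI is 5.0%, 4.6% and 4.2%, against 2.5% for one test.

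**4. If both are required.** The error is held. Power at N = 128 and r = 0 with independent endpoints is the square of the single-test power: 0.801² = 0.64 at d = 0.5. Over endpoint correlation 0 to 0.7:

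| d | r = 0 | r = 0.5 |
|---|---|---|
| 0.5 | 64-71% | 81-85% |
| 0.4 | 38-49% | 54-63% |
| 0.3 | 15-27% | 24-37% |

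At d = 0.5, joint power reaches 80% once r is about 0.41 to 0.49, depending on the endpoint correlation.

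**5. If Holm is used.** A given endpoint passes if its p < 0.025, or if its p < 0.05 and the other endpoint has p < 0.025. With independent endpoints, d = 0.5 and r = 0, its power is 0.712 + (0.801 − 0.712) × 0.712 = 0.78. Over endpoint correlation 0 to 0.7, with equal effects on both endpoints, it is about 76-78%, 55-56% and 32% at d = 0.5, 0.4 and 0.3. The lower figures of 71%, 50% and 29% apply only if that endpoint alone has an effect.

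**The case against.** **Reporting.** The plan does not contain the word only and does not say that means or SDs will be withheld. It promises standard statistical calculations (section 4.1), allows that de-identified data may be shared for meta-analyses (7.4), undertakes to seek publication (9) and plans a final report to the Ethics Committee (5.7). A reader might infer that non-significant results will be suppressed, and the documents do not support that. What stands is narrower: significance is the sole stated trigger for an effect size, and none of these sections promises an estimate or interval.

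**Error rate.** A reader might infer that the trial runs a false-positive risk near 10%. The documents do not support that either. Hypothesis 1 joins alliance and adherence, which favours requiring both, and error is then held. The 8.4-9.8% arises only under a rule the plan does not state. What stands is a request to state the rule.

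**Power.** A reader might infer that the sample size is wrong. It is not: 80% reproduces for one test, and the plan never claims it for two. Any shortfall rests on assumed correlations and disappears at d = 0.5 with r = 0.5. The low figures at d = 0.3 and 0.4 mostly reflect planning at the top of the cited range, since single-test power there is already 39% and 61% at r = 0.

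**Weight.** This is a pilot, so strict error control matters less than in a pivotal trial. I accept that. For the same reason, unfiltered estimates matter more.

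**Conclusion.** The reporting rule should be changed. At 64 per group and r = 0 it inflates the average reported effect by about 0.18, 0.11 and 0.07 at true d = 0.3, 0.4 and 0.5 (0.48 − 0.3, 0.51 − 0.4, 0.57 − 0.5) and leaves a given endpoint without an effect size in 61%, 39% and 20% of trials. With r = 0.5 both problems are smaller but remain. These figures assume that the sentence is applied as written and that the cited d is unadjusted.

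The missing rule for Hypothesis 1 and the unnamed STAR score are real but secondary. They call for clarification and do not show an error in the plan. The power statement is correct and lacks only a label.

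**What to change.** 1. Replace the effect-size sentence in section 4.1 with: *The adjusted mean difference, standardised effect and 95% CI are reported for every primary and secondary endpoint regardless of p-value.*
2. Name one STAR score as primary: patient or clinician version, and total or subscale.
3. State the rule for Hypothesis 1 before data are seen. Given its wording, the natural choice is: *Hypothesis 1 is supported only if both STAR and BARS favour MI at two-sided 0.05.* If a claim on one endpoint is to be allowed, use Holm at a familywise two-sided 0.05 and claim only what passes. The choice is the investigators'.
4. Label the 80% as single-endpoint power at d = 0.5. Give the power at N = 128 for the chosen rule over d = 0.3 to 0.5, with the assumed baseline-outcome correlation.

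The cost is SAP wording and a less favourable stated power. No extra patients are required. If the investigators nevertheless wanted 80% under the chosen rule at d = 0.5 and r = 0, the total would be about 154-168 with both endpoints required, or about 136 for a given endpoint under Holm with equal effects on independent endpoints. A total of 156 would apply under Holm only if that endpoint alone had an effect.

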In our **study intervention**, patients should receive four sessions of motivational interviewing within two weeks. Throughout the MI sessions, interviewers use common MI techniques including open-ended questions, affirmations, reflections, summaries, asking permission, expressing empathy, supporting self-efficacy, etc. Interviewers are clinical psychologists who received MI training immediately prior to the study.

In the **control intervention** patients should also be given four sessions, in which no MI techniques take place. They will be carried out in the sense of supportive conversations. Supportive conversations aim to promote stabilization of the patient's current state without pursuing a goal set by the therapist. Supportive therapy includes tasks such as assistance with everyday requirements, emotional relief in the event of problems, or the provision of a reliable relationship. The topics are preferably defined by the patient. The clarification and processing of conflicts and problems that underlie the psychopathology is not usually the subject of therapy (Weierstall & Schonauer, 2016).

Since we want to check whether the patients really benefit from the specific intervention and not from getting more speaking time, the patient in the control group will also be given four conversations. It is known that supportive conversations can have a certain effect on the well-being and recovery process of patients, as the therapeutic relationship, i.e. appreciation, attention and/or attention, is an important efficacy factor (e. g. Grawe, 1995).

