### **3 STUDY POPULATION AND STUDY PROCEDURES**

#### **3.1 Inclusion and exclusion criteria, justification of study population**

As the aim of the study is to improve psychotherapeutic treatment in the acute phase of psychosis, the inclusion of patients suffering from this disorder is necessary and cannot be studied in healthy people.

We will recruit newly admitted inpatients from the Psychiatric University Hospital with a diagnosis of a psychotic spectrum disorder (schizophrenia, schizoaffective disorder, acute psychotic

disorder, psychosis not otherwise specified, bipolar disorder with psychotic features, major depression with psychotic features). Patients are recruited within the first three days of hospitalization to test psychotherapeutic interventions in the acute phase of illness.

Patients fulfilling all of the following inclusion criteria may be enrolled in the study:

- Informed consent as documented by signature
- Male and female patients from PUK inpatient units between 18 and 65 years of age
- ICD-10 diagnosis of psychosis (F2) meeting DSM-IV criteria
- Fluent in German and able to understand the instructions

The presence of any one of the following exclusion criteria will lead to exclusion of the participant:

- Organic schizophrenia-like disorder (ICD: F0.6)
- Cognitive impairments: strongly below average values in more than two cognitive tests (percentage rank < 5)
- Drug or alcohol abuse during treatment
- Previous enrolment in the current study
- Enrolment of the investigator, his/her family members, employees and other dependent persons.
- During study: Complete stop of taking antipsychotic medications without the consent of the attending physician.

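### The planned comparison of patients who benefit strongly or little from MI leaves benefit undefined and, if it means change within the MI arm, cannot separate markers of general recovery from markers of MI response

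*Combined protocol and SAP*

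**What the plan says.** Section 4.1 declines a gender analysis and then adds that "it is planned to conduct a group comparison between patients who benefit strongly from MI and those who benefit little", and that the aim is "to investigate possible discriminatory factors as part of this". It names no outcome, cut-off, candidate factor or test, and mentions neither the control arm nor an interaction.

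The only patient-level outcome defined in the plan is in the additional calculations of the same section: "The treatment outcome is defined as the delta between symptoms before and after the intervention and serves as dependent variable". That definition belongs to a separate regression on days of hospitalization and/or PANSS total, which has no treatment-arm term.

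The three hypotheses are handled differently. For hypothesis 1, "we will use an ANCOVA to analyze the treatment effect of motivational interviewing compared to supportive counseling, with baseline values used as covariates"; hypotheses 2 and 3 have the same analysis. Section 2.4 explains why there is a control arm: "Since we want to check whether the patients really benefit from the specific intervention and not from getting more speaking time". It adds: "It is known that supportive conversations can have a certain effect on the well-being and recovery process of patients".

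On the population, section 3.1 says: "Patients are recruited within the first three days of hospitalization". One exclusion criterion reads: "During study: Complete stop of taking antipsychotic medications without the consent of the attending physician".

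**The concern.** Benefit from MI is the difference between a patient's outcome with MI and the same patient's outcome without it. A parallel-group trial shows only one of the two. Any sorting of MI recipients by their own results therefore mixes the MI effect with the course of the episode, ward treatment and non-specific attention. Section 2.4 recognises the last of these and adds the supportive-counseling arm to remove it. As far as it is described, the strong-versus-little comparison does not use that arm.

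A factor that goes with faster recovery under any care could then be reported as a marker of who responds to MI, even if MI helps everyone equally or nobody. No marker-by-treatment interaction is planned elsewhere that would expose the error. The protocol describes the study as a pilot for larger trials, so a wrong statement about who benefits could influence later design.

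**Working it through.** **1. The plan's own figure.** For two equal groups d = 2f = 2 × 0.25 = 0.5. With two-sided alpha 0.05 and 80% power, the normal approximation gives n = 2(1.96 + 0.84)²/0.5² ≈ 63 per arm. The exact t test gives 63.8, so 64 per arm and N = 128, with power 80.1%. The stated sample size reproduces and is not in question.

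**2. Inputs for the comparison.** From the plan: 64 per arm, 1:1 allocation, d = 0.5, two-sided 0.05. Assumed, because the documents are silent: benefit means change, strong and little are the halves above and below the MI-arm median, residual SD is 1, and there is one 50/50 factor that shifts change by b SD equally in both arms. The MI effect is the same for everyone, so the correct answer is that the factor does not predict MI response.

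**3. Why the split flags the factor.** A uniform MI effect moves every MI patient and the median together, so it drops out of the split. Only b remains. The chance of falling in the upper half is about Φ(b/2) with the factor and 1 − Φ(b/2) without it. With about 32 patients per factor level, the null standard error of the difference is √(0.25 × 2/32) = 0.125, so z ≈ [2Φ(b/2) − 1]/0.125. For b = 0.5, Φ(0.25) = 0.599 and z = 0.197/0.125 = 1.58, so the rejection probability is about Φ(1.58 − 1.96) = 35%. Simulation agrees closely:

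| Prognostic effect b (SD) | MI-arm split, uncorrected chi-square | MI-arm split, continuity-corrected | Same split in control arm, uncorrected | Arm-by-factor interaction |
|---|---|---|---|---|
| 0.3 | 17% | 11% | 18% | about 5% |
| 0.5 | 39% | 29% | 39% | about 5% |
| 0.8 | 74% | 65% | 71% | about 5% |
| 1.0 | 88% | 83% | 89% | about 5% |

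The control-arm column is the telling one: the procedure finds MI-benefit factors just as often in patients who never received MI.

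**4. A continuous factor (t test between halves).** A purely prognostic factor with slope 0.3, 0.5 or 0.7 SD is flagged in 44%, 85% and 98% of runs in the MI arm and in 43%, 84% and 98% in the control arm, against about 5% for the interaction. A factor that predicts only MI response, with slope 0.3 or 0.5, is flagged by the split in 44% and 84%. The split therefore responds to both kinds of factor in the same way. When the slopes oppose (prognostic −0.5, MI-predictive +0.5), it finds the true MI marker in 5% of runs; the interaction test finds it in 79%.

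**5. What the interaction test can detect.** For a 50/50 binary factor there are four cells of 32, so the standard error is √(4/32) = 0.354, twice the √(2/64) = 0.177 of the main comparison. An interaction of 0.3, 0.5 or 0.8 SD gives a ratio of 0.85, 1.41 or 2.26, and power of about 13%, 29% and 61%. For a continuous factor, power is about 37% and 79% at slope differences of 0.3 and 0.5 SD. No multiplicity adjustment is included.

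**The case against.** The strongest reply is that this is one exploratory sentence that specifies almost nothing, and that the trial's conclusions come from ANCOVAs that do use the control arm. That stands, and it limits the weight of the point. Several stronger readings are tempting and are not supported:

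- A reader might infer that the plan defines benefit as pre-post change. It does not. The delta is defined for the additional regression only, and carrying it over is plausible but undocumented. The demonstrable defect is that benefit is undefined. Still, any patient-level measure taken within the MI arm meets the same obstacle.
- A reader might infer that the comparison finds recovery markers in place of MI markers. It picks up both and cannot tell them apart.
- A reader might take all patients to be medicated. Section 3.1 only excludes unapproved complete cessation of antipsychotics; medication at entry is not required.
- A reader might see the same flaw in the additional regression. That analysis asks how length of stay and initial severity relate to outcome, which is a legitimate prognostic question. Because arm is randomised, leaving it out mainly costs precision.
- A reader might infer that markers found here will select patients for the multicentre trial. Section 1 speaks of acceptance, feasibility and effectiveness data, not of selection markers.

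It is also fair to say that the false-positive figures are conditional. The highest rates need one binary factor that shifts change by 0.8 to 1.0 SD, more than the assumed treatment effect. At 0.3 to 0.5 SD the range is 11% to 39%, depending on the continuity correction.

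**Conclusion.** The point holds in a limited form. The strong-versus-little comparison rests on a quantity that the trial cannot observe and the plan does not define. If it is carried out as a split on change within the MI arm, factors it flags cannot be read as markers of MI response. Under the stated assumptions a purely prognostic factor is flagged in about 17% to 88% of trials (11% to 83% with continuity correction), as often as in the control arm, against about 5% for the interaction test. These rates illustrate the mechanism and do not predict this trial's results, because the factor's effect, the median split and the single factor are all assumed. The consequence is confined to exploratory statements about who benefits. Hypotheses 1 to 3 and N = 128 are unaffected.

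**What to change.** In section 4.1, replace the strong-versus-little comparison with arm-by-factor interaction terms added to the ANCOVA already planned, using both arms and baseline adjustment. Name the outcome and a short list of candidate factors in advance, and label the analysis exploratory. At each level of a factor, report the MI-minus-control difference with its confidence interval.

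In the additional regression, add treatment arm as a covariate for precision, and describe the results as predictors of course, not of MI response.

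The change needs only SAP wording and a few model terms on data already being collected. The real cost is low power: about 13%, 29% and 61% for binary-factor interactions of 0.3, 0.5 and 0.8 SD. Most true modifiers of moderate size would be missed, so a non-significant interaction should not be reported as evidence that MI works equally well for everyone.
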